12.3 Data Handling

Data quality may be monitored via centralized data monitoring and edit checks. Centralized data monitoring may include individual subject and aggregate data analysis and review to identify outliers for confirmation by the site.

12.4 Case Report Form (CRF) & Source Documents

All study staff will be trained on the protocol requirements and CRF completion. It is the responsibility of the Investigator to maintain adequate and accurate CRFs designed by Laborie to record all observations and other data pertinent to the clinical investigation. All CRFs should be completed in their entirety in a neat, legible manner to ensure accurate interpretation of data. Should a correction be made, the information to be modified must not be overwritten. The corrected information will be transcribed by the authorized person using the correction section of the CRF. Source documents templates are present at the sites. Data from the source documents should be entered into the CRF after each subject's visit.

12.5 Record Retention

Each Investigator must maintain accurate, complete, and current records relating to the conduct of the study. The final responsibility for maintaining such records remains with the Investigator. These records include, but not limited to:

- All signed agreements
- IRB approval letters
- Signed ICF
- Records of each subject's case history, including study required CRFs,
- Signed delegation of authority logs
- Any other records applicable to the clinical study

An investigator or sponsor shall maintain the records required by 21 CFR Part 812.140 during the investigation and for a period of 2 years after the investigation is terminated or completed. The Investigator must maintain confidential all study documentation and take measures to prevent accidental or premature destruction of these documents. All essential documents from the Investigator will be kept in the Investigator binder. All sponsor essential documents will be kept in the study master file. The investigator and sponsor shall also maintain a record of their location of the respective essential documents. If the Investigator's personal situation is such that archiving can no longer be ensured by him/her, the Investigator shall inform the Sponsor and the relevant records shall be transferred to a mutually agreed upon designee.

12.6 Performance Monitoring

A quality control procedure will be reviewed prior to study procedure execution to ensure that all equipment is working within its specified performance. In the event that this is not the case, alternative equipment will be supplied where possible provided the alternative equipment will not jeopardize the

ILLUMINATE Clinical Study Protocol

outcome of the study data. Monitors will periodically check CRF data to ensure all fields are entered as far as possible and inquire as to whether any usability issues are being encountered as the study progresses.

13 MONITORING, AUDITING, AND INSPECTING

13.1 Study Monitoring Plan

The Investigator agrees to provide reliable data and all information requested by the clinical trial protocol (with the help of the Case Report Form [CRF] or other appropriate instrument) in an accurate and legible manner according to the instructions provided and to ensure direct access to source documents to Sponsor representatives.

The Sponsor of this Clinical Trial is responsible to Health Authorities for taking all reasonable steps to ensure the proper conduct of the Clinical Trial Protocol as regards ethics, Clinical Trial Protocol compliance, integrity and validity of the data recorded on the Case Report Forms. Thus, the main duty of the Monitoring Team is to help the Investigator and the Sponsor maintain a high level of ethical, scientific, technical, and regulatory quality in all aspects of the Clinical Trial.

At regular intervals during the Clinical Trial, the site will be contacted, through monitoring visits, letters, or telephone calls, by a representative of the Monitoring Team to review study progress, Investigator and subject compliance with Clinical Trial Protocol requirements, and any emergent problems (as per the sponsor's monitoring plan). During these monitoring visits, the following but not exhaustive list of points will be scrutinized with the Investigator: subject informed consent, subject recruitment and follow-up, Serious Adverse Event documentation and reporting, outcome events documentation and reporting, and quality of data.

13.2 Auditing and Inspecting

For the purpose of ensuring compliance with the Clinical Trial Protocol, Good Clinical Practice and applicable regulatory requirements, the Investigator should permit auditing by or on the behalf of the Sponsor and inspection by applicable regulatory authorities.

The Investigator agrees to allow the official inspectors to have direct access to his/her study records for review, who are bound by professional secrecy and as such, are not entitled to disclose any personal identity or personal medical information.

The Investigator will make every effort to help with the performance of the audits and inspections, granting access to all necessary facilities, data, and documents to the designated auditors/inspectors.

As soon as the Investigator is notified of a future inspection by the authorities, the Investigator will inform and authorize the Sponsor to participate in the planned inspection.

The confidentiality of the data verified, and the protection of the subjects should be respected during these inspections.

Any result and information arising from the inspections by the regulatory authorities will be immediately communicated by the Investigator to the Sponsor. The Investigator shall take appropriate measures required by the Sponsor to take corrective actions for all problems found during the audit or inspections.

ILLUMINATE Clinical Study Protocol**14 DEVIATIONS**

All departures from the approval protocol shall be documented by the investigator. All deviations will be recorded on the subject CRF, and a deviation report will be sent to Laborie and the ethics board, as required. Timelines for notification will be subject to IRB standard operation procedures. Deviations will be reviewed and signed off by the sponsor. If deviations are observed/reported that significantly affect or have the potential to significantly affect human subject protection or reliability of the trial results, then Laborie will conduct a root cause analysis and implement appropriate corrective and preventative actions.

Significant risk deviations from the approved protocol are those which impact subject rights and safety, or data integrity and data security. Serious or repeated protocol deviations on the part of the investigator may be grounds for termination of the clinical investigation. The sponsor may also consider other corrective actions including protocol re-training, site visit, conference call or a formal warning letter.

Investigators may request prior, written approval for a study deviation or change in protocol. A protocol amendment may be required, and IRB/regulatory authorities notified where applicable.

Deviations from the protocol to protect the rights, safety, and well-being of subjects under emergency circumstances may proceed without prior approval from the sponsor, IRB, or regulatory authority. Such deviations shall be documented and reported to the sponsor and IRB as soon as possible.

15 AMENDMENTS

If there are any significant changes to the protocol during the clinical study application process or during the length of the clinical study in progress, the protocol with amendments will be completed and sent to the IRB for notification and review. If an amendment is made to the protocol during an ongoing study, the amended protocol will be sent to the applicable institution within the timelines required. The Investigator should not implement any deviation from or changes to the clinical protocol without agreement by the Sponsor and prior review (and documented approval/favorable opinion) from the IRB of an amendment, except when necessary to eliminate an immediate hazard(s) to a clinical study subject. In some instances, an amendment may require a change to the Informed Consent Form. The Investigator must receive an IRB approval/favorable opinion concerning the revised Informed Consent Form prior to implementation of the change.

16 STUDY ADMINISTRATION**16.1 Funding Sources and Conflicts of Interest**

Laborie will be the sponsor and the financial details are covered in the Investigator Agreement.

16.2 Subject Stipends or Payments

Subjects will be offered a stipend for their participation in the study. The Sponsor has covered this study by means of an insurance covering bodily injury or property damage arising out of the clinical trial. The certificate of insurance evidencing the coverage, insurance company, policy number and the sum insured are provided in the Study's File.

ILLUMINATE Clinical Study Protocol**16.3 Committees**

A Data Monitor Committee will not be utilized in this study based on the evaluation of the level of potential risks.

17 ETHICS AND REGULATORY APPROVAL

This study will not begin until the appropriate approvals from the IRB have been obtained. Any additional requirements imposed by the IRB will be followed. This study will be conducted in compliance with all laws and regulations governing human studies, as well as any applicable guidelines.

The study will be registered on www.clinicaltrials.gov, as appropriate.

18 PUBLICATION POLICY

The results of the study may be submitted for publication, whether peer-reviewed or marketing materials. Publication rights and details are covered in the Investigator Agreement, there may be other authors involved in the creation of the publication.

The data and results from the trial are the sole property of the Sponsor. The Sponsor shall have the right to access and use all data and results generated during the study. The Investigators will not use the study/investigation-related data without the written consent of the Sponsor for any other purpose than for study/investigation completion or for generation of publication material, as referenced in the Study Agreement/Investigator Agreement.

The Sponsor acknowledges that the trial's Principal Investigators intend to publish a multi-center publication regarding the study/investigation results, and numerous secondary publications. The Sponsor must receive any proposed publication and/or presentation materials at least 30 days prior to the proposed date of the presentation or the initial submission of the proposed publication in order for the materials to be reviewed by the Sponsor in compliance with the Sponsor's publication policy set forth in the Study Agreement/Investigator Agreement.

The study will be registered on the ClinicalTrials.gov website upon approval by an IRB in order to meet the criteria of the International Committee of Medical Journal Editors. Institution(s) and/or Principal Investigator(s) shall not take any action to register the trial.

19 RELATED STUDY DOCUMENTS**19.1 Informed Consent Form**

[REDACTED]

The purpose of the SAP is to provide clarification about the statistical considerations and methods to be implemented for the analysis of data. The statistical analysis plan has been reviewed by an independent statistician with no access to or knowledge of accumulating trial data. It is based on version B of the CIP [REDACTED]. Any revisions to this SAP will be made prior to database lock and reasons for such revisions will be described in the final clinical study report.

2 Abbreviations

Abbreviation or Acronym	Term/Meaning
ADE	adverse device effect
AE	adverse event
ASADE	anticipated serious adverse device effect
CRF	case report form
CIP	clinical investigation plan
DD	device deficiency
EC	ethics committee
SADE	serious adverse device effect
SAE	serious adverse event
USADE	unanticipated serious adverse device effect

3 Objectives and Endpoints

3.1 ILLUMINATE Clinical Study Objectives

The ILLUMINATE Clinical Study has a primary and a secondary objectives.

3.1.1 Primary objective:

- Obtain normative datasets for traditional measures of anorectal function with an air charged HRAM catheter in healthy subjects using the IAPWG standardized testing protocol and London classification for ARM measurement

ILLUMINATE Clinical Study Statistical Analysis Plan

3.1.2 Secondary objective:

- Qualitatively compare the performance of air charged and solid state HRAM catheters in determining normative values for traditional measures of anorectal function in a subset of study subjects using the IAPWG standardized testing protocol and London classification for ARM measurement.

3.2 Study Endpoints

3.2.1 Primary endpoints:

Each subject will undergo a standard ARM procedure using the Solar Catheter in accordance with standard of care, device IFU and the IAPWG standardized testing protocol and London classification for ARM measurement where, at minimum, the following parameters are collected:

- Functional anal canal length, cm
- Anal resting pressure, mmHg
- Anal squeeze pressure, mmHg
- Push pressure, mmHg
- Cough pressure, mmHg

Additionally, the following parameters may be collected:

- Rectal pressure increase, mmHg
- Anal pressure decrease, mmHg
- First constant sensation
- Defecatory desire volume, ml
- Maximum tolerated volume, ml

3.2.2 Secondary endpoints:

Will be measured by recording specific anorectal pressure parameters in each healthy individual using SolarTM air charged catheter and UniTipTM solid state catheter. The goal is to compare the readings recorded for each parameter by both catheters in the same healthy individual. The parameters to be recorded for comparison include, at minimum, the following:

- Functional anal canal length, cm
- Anal resting pressure, mmHg
- Anal squeeze pressure, mmHg
- Push pressure, mmHg
- Cough pressure, mmHg

Additionally, the following parameters may be collected:

- Rectal pressure increase, mmHg
- Anal pressure decrease, mmHg
- First constant sensation
- Defecatory desire volume, ml
- Maximum tolerated volume, ml

[REDACTED]
[REDACTED]
[REDACTED]
[REDACTED]

- [REDACTED]
- [REDACTED]
- [REDACTED]

[REDACTED]
[REDACTED]

Safety:

Collection and characterization of all reported adverse events from the start of study to study exit. Adverse event details to be collected can be found on [REDACTED] ILLUMINATE Study CRFs.

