The Solar catheter and the UNITIP catheter are Laborie-designed HRAM catheters with different types of pressure sensors that use the same data analysis algorithms in the Laborie Solar GI HRAM or Solar Compact HRM system. It is important to understand the relative performance of the two types of catheters when determining traditional anorectal function parameters. Therefore, a secondary rationale for the clinical study is to qualitatively compare the performance of the Solar catheter and the UNITIP catheter in determining values for traditional measures of anorectal function in a subset of the study subjects using the IAPWG standardized testing protocol and London classification. To achieve this, a second ARM procedure with the UNITIP catheter will be carried out on some of the study subjects under the IAPWG standardized testing protocol and London classification. Measurement values obtained from the second ARM procedure will be qualitatively compared to that from the first ARM procedure to understand the relative performance of the two catheters.

ILLUMINATE Clinical Study Protocol**3.3 Medical Device**Solar Catheter [REDACTED]

[REDACTED]

[REDACTED]

[REDACTED]

ILLUMINATE Clinical Study Protocol

[REDACTED]

[REDACTED]

[REDACTED]

ILLUMINATE Clinical Study Protocol

UNITIP™ HRAM Catheter

[REDACTED]

[REDACTED]

[REDACTED]

[REDACTED]

ILLUMINATE Clinical Study Protocol

Solar GI HRAM system

[REDACTED]

[REDACTED]

[REDACTED]

ILLUMINATE Clinical Study Protocol

Solar Compact HRM System [REDACTED]

[REDACTED]

[REDACTED]

[REDACTED]

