3.3 Procedure Related Terminologies

Healthy volunteers who are eligible for anorectal manometry measurements may undergo high-resolution anorectal manometry (HRAM) procedure to achieve study objectives.

- I. [REDACTED]
 - [REDACTED]
 - [REDACTED]
 - [REDACTED]
 - [REDACTED]
 - [REDACTED]
 - [REDACTED]
 - [REDACTED]
 - [REDACTED]
 - [REDACTED]
 - [REDACTED]
 - [REDACTED]
 - [REDACTED]
 - [REDACTED]
 - [REDACTED]
 - [REDACTED]
 - [REDACTED]
- [REDACTED]
 - [REDACTED]
- [REDACTED]
 - [REDACTED]
- [REDACTED]
 - [REDACTED]
- [REDACTED]
 - [REDACTED]
- [REDACTED]
 - [REDACTED]

ILLUMINATE Clinical Study Statistical Analysis Plan

4 Study Design

This is a prospective, multi-center, open label post-market study. The treatment arm (i.e., ARM with Solar catheter) will consist of approximately 81 asymptomatic individuals (volunteers) recruited from the intended patient population. A subset of up to 40 study subjects will be evaluated with two ARM catheters (i.e., Solar and UNITIP catheters). The order of application of the two catheters will not be randomized. A washout period between procedures will be determined by the investigator according to their standard practice and used to mitigate potential confounding impact of patient fatigue on the primary objective.

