4.2 Sample Size Determination

This is a descriptive study aimed at estimating parameters used in diagnostic evaluation of gastrointestinal disorders. No formal hypothesis tests are planned for any endpoint, and descriptive statistics and exploratory analyses will be used in reporting outcomes for all endpoints. The sample size is calculated for estimating the mean for specific parameters with a specified precision.

[illegible]

ILLUMINATE Clinical Study Statistical Analysis Plan

5 Statistical Analysis

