5.1 General Considerations

Descriptive statistics will be used to analyze data from this study. Continuous variables will be summarized with means, median, standard deviations, IQR, sample size (N), minimums, and maximums. If included, categorical variables will be summarized in frequencies and percentages in the category of interest. Statistical analysis will be conducted in SAS or other validated statistical software package.

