5.5 Analysis of Study Endpoints

Results provided from the software analysis of the study endpoints will be summarized and reported. [REDACTED]

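### Same-person catheter comparison: the visible text names only marginal summaries, which cannot show whether the two catheters agree in an individual

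*SAP*

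**What the plan says.** - **Goal.** SAP 3.2.2, on the secondary endpoints: "The goal is to compare the readings recorded for each parameter by both catheters in the same healthy individual". Protocol 9.1 gives the same goal.
- **Type of comparison.** SAP 3.1.2: "Qualitatively compare the performance of air charged and solid state HRAM catheters in determining normative values", in a subset of subjects. Protocol 3.2: "Measurement values obtained from the second ARM procedure will be qualitatively compared to that from the first ARM procedure". Protocol 4 also calls it qualitative.
- **Statistics named.** SAP 5.1: "Continuous variables will be summarized with means, median, standard deviations, IQR, sample size (N), minimums, and maximums". Protocol 11.1 has the same list. SAP 4.2 adds: "No formal hypothesis tests are planned for any endpoint, and descriptive statistics and exploratory analyses will be used".
- **Endpoint analysis.** SAP 5.5 has one visible sentence, "Results provided from the software analysis of the study endpoints will be summarized and reported"; the rest is redacted. Text after the parameter lists in SAP 3.2.2 and after SAP 5.6 is also blacked out.
- **Size and order.** SAP 4: "A subset of up to 40 study subjects will be evaluated with two ARM catheters". No minimum is visible. SAP 4.1 and Protocol 11.3 fix the order, with Solar first in everyone.
- **Missing values.** Under SAP 5.3 a missing value drops out of the analysis it belongs to. No visible rule limits the catheter comparison to subjects with both readings.

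**The concern.** The goal concerns differences within a person, but every statistic named describes one variable at a time. No visible passage names a within-person difference, a bias with a confidence interval, limits of agreement or an acceptable difference.

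Protocol 9.1 says the results are meant to help physicians interpret pressures and choose between catheters. For that, a reader needs to know how far the two readings can lie apart in one person. Two catheters can have matching means and SDs and still disagree widely from subject to subject. If the report gave only one column of summaries per catheter, readers could take similar columns as evidence of interchangeability, which they are not.

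**Working it through.** **Inputs.** The documents give up to 40 pairs (SAP 4), the list of statistics (SAP 5.1) and the fixed order (SAP 4.1). They do not give the SD of any parameter, the correlation ρ between catheters, or the SD of the within-person differences (SDd). Results are therefore in SD or SDd units, over a range of assumed ρ. The visible text has no calculation for the paired subset, so there is no planned figure to reproduce; the target of 81 rests on estimating a mean for the primary aim.

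**Step 1: what the marginal tables leave open.** In complete pairs, the difference between the two means equals the mean paired difference, so the tables give the point estimate of bias. The spread of the differences is another matter. With equal SDs,

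SDd = SD × √(2(1 − ρ)), and limits of agreement = bias ± 1.96 × SDd.

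None of the listed statistics contains ρ. The same means and SDs therefore fit all of these:

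| ρ (assumed) | SDd / SD | 95% limits around the bias |
|---|---|---|
| 0.5 | 1.000 | ±1.96 SD |
| 0.7 | 0.775 | ±1.52 SD |
| 0.8 | 0.632 | ±1.24 SD |
| 0.9 | 0.447 | ±0.88 SD |

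From ρ = 0.9 to ρ = 0.5 the limits widen by a factor of 1.96 / 0.88 ≈ 2.2, with no change in the tables.

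**Step 2: what a paired analysis would deliver.** With n complete pairs, the 95% half-width for the bias is t(0.975, n−1) × SDd / √n. The standard error of each limit is SDd × √(1/n + 1.96² / (2(n−1))), multiplied by the same t quantile.

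At n = 40, t ≈ 2.023:
- bias: 2.023 / √40 = 0.32 SDd
- each limit: 2.023 × √(0.0250 + 0.0493) = 2.023 × 0.2725 = 0.55 SDd

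| Complete pairs | Bias, 95% half-width | Each limit, 95% half-width |
|---|---|---|
| 40 | 0.32 SDd | 0.55 SDd |
| 30 | 0.37 SDd | 0.65 SDd |
| 20 | 0.47 SDd | 0.81 SDd |

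The 40-pair row is the best case, because 40 is a maximum.

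**Step 3: what pairing cannot repair.** Every UNITIP reading follows a Solar reading. The mean paired difference is therefore the catheter effect plus any order or fatigue effect, and no analysis of these data separates the two.

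**The case against.** The strongest objection is the redaction. SAP 5.5 is where a paired method would stand, and blacked-out text cannot be counted as absent. SAP 5.1 covers general considerations only; a within-person difference is itself a continuous variable, so its mean and SD could be reported under that section. SAP 4.2 also allows exploratory analyses. This stands, and it makes the point conditional.

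Three stronger readings are tempting, and the documents do not support them.

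- **A reader might infer that the plan discards the pairing.** No passage says so. The stated goal is within-person, and Protocol 3.2 sets second-procedure values against first-procedure values.
- **A reader might infer that Solar in 81 subjects will be set against UNITIP in 40.** The secondary objective places the comparison in the subset, so this is only one possible reading. No visible rule says who enters the subset, but in complete pairs that mainly affects whom the result represents, provided entry does not depend on the Solar reading itself.
- **A reader might claim a large gain in precision.** Treating 81 and 40 as independent gives 1.96 × √(1/81 + 1/40) = 0.379 SD. But the 40 are among the 81, so the variance is 1/81 + 1/40 − 2ρ/81. At ρ = 0.7 the half-width is 0.278 SD, against 1.96 × √(2 × 0.3 / 40) = 0.240 SD for pairs, about 14% narrower. At ρ = 0.5 both equal 1.96 × √(1/40), so there is no gain. The plan also shows no interval for a group difference that could be improved.

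It is also fair to say that the study is descriptive, the comparison is secondary, and a qualitative aim does not call for a test. That is accepted: estimates with intervals remain descriptive, and the primary aim is unaffected.

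**Conclusion.** The point holds in conditional form. The visible text sets a within-person goal and names only statistics that cannot answer it. The same tables would fit limits of agreement from ±0.88 SD to ±1.96 SD, assuming equal SDs and correlations of 0.9 and 0.5. This arithmetic does not depend on what SAP 5.5 contains; whether the plan has a gap does, so confidence is medium.

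The case for change rests on agreement, not on precision. The change should be made because it lets the analysis meet the plan's own secondary goal at almost no cost. It does not touch the primary normative aim, and the absence of a hypothesis test is not a fault.

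**What to change.** Unless the redacted part of SAP 5.5 already does so, state there, for each parameter and only in subjects with both readings:

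1. the number of complete pairs and the mean paired difference with its 95% CI;
2. a Bland-Altman plot;
3. the 95% limits of agreement with a CI for each limit.

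No hypothesis test is needed. Add two items to the report:

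- a statement that Solar was always first, so the mean difference combines catheter with order or fatigue and its CI does not cover that uncertainty;
- a table of Solar values in subset and non-subset subjects, to show how representative the subset is.

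If SAP 5.5 already has a paired method, a cross-reference from SAP 3.2.2 would be enough, along with these two items if they are absent.

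The cost is SAP wording and standard code, with no added subjects, visits or procedures. The SAP's opening statement of purpose allows revision before database lock, with reasons given in the final report.
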